2	Requires infusion interruption but responds promptly to symptomatic treatment (eg, antihistamines, NSAIDs, narcotics, IV fluids); prophylactic medications indicated for ≤ 24 hours.	
First occurrence: Stop infusion and initiate appropriate medical measures (eg, IV fluids, antihistamines, NSAIDs, antipyretics, narcotics) per institutional preferences.
 
Monitor vital signs until medically stable.
 
If symptoms resolve within 1 hour, infusion may be resumed at 50% of the original infusion rate.
 
Subsequent occurrences (after recommended prophylaxis): Permanently discontinue study treatment.
	
Premedicate at least 30 minutes before infusion with antihistamines (eg, diphenhydramine 50 mg PO) and an antipyretic (eg, acetaminophen/paracetamol 500-1000 mg PO).
 
Additional supportive measures may be acceptable (per institutional preference) but should be discussed with medical monitor.
 
Next infusion should start at 50% of the original infusion rate. If no reaction, rate of infusion can be increase by 25% every 15 minutes until a rate of 100% has been reached. Subsequent infusions can begin at 100%.

3 or 4	
Grade 3: Prolonged (ie, not rapidly responsive to symptomatic medication and/or brief interruption of infusion); recurrence of symptoms following initial improvement; hospitalization indicated for other clinical sequelae (eg, renal impairment, pulmonary infiltrates).
 
Grade 4: Life-threatening; pressor or ventilatory support indicated.
	
Stop infusion and initiate appropriate medical therapy (eg, IV fluids, antihistamines NSAIDs, antipyretics, narcotics, oxygen, pressors, epinephrine, corticosteroids) per institutional preferences.
 
Monitor vital signs frequently until medically stable.
 
Hospitalization may be indicated.
	Permanently discontinue study treatment.

Note: Per NCI CTCAE v5.0, appropriate resuscitation equipment should be available at the bedside and a physician readily available during the period of study treatment administration ([NCI 2017](#)).

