9.3. Recording and Follow-Up of Adverse Events and/or Serious Adverse Events

Adverse Event and Serious Adverse Event Recording

- An AE/SAE that begins or worsens after informed consent is signed should be recorded on the Adverse Event Form in the eCRF. AEs/SAEs should be reported for randomized participants, but only SAEs need to be reported for screen failure participants. For randomized participants, conditions that were present at the time informed consent was given should be recorded on the Medical History eCRF. For detailed information refer to the eCRF guidelines.
- When an AE/SAE occurs, it is the responsibility of the investigator to review all documentation (eg, hospital progress notes, laboratory reports, and diagnostic reports) related to the event.
- The investigator (or delegate) will then record all relevant AE/SAE information in the eCRF.
- It is **not** acceptable for the investigator to send photocopies of the participant's medical records in lieu of completing the Adverse Event Form in the eCRF.
- There may be rare instances when copies of medical records for certain cases are requested. In this case, all participant identifiers, with the exception of the participant number, will be redacted by the site staff on the copies of the medical records before submission. These records can be submitted to Incyte Pharmacovigilance by email/fax per the contact information listed in the Study Reference Manual.
- The investigator will attempt to establish a diagnosis of the event based on signs, symptoms, and/or other clinical information. Whenever possible, the diagnosis (not the individual signs/symptoms) will be documented as the AE/SAE. When a clear diagnosis cannot be identified, each sign or symptom should be reported as a separate AE/SAE.

To the extent possible, each AE/SAE should be evaluated to determine the following:

- The severity grade (CTCAE v5.0 Grade 1 to 5). See below for further instructions on the assessment of intensity.
- Whether there is at least a reasonable possibility that the AE is related to the study treatment: suspected (yes) or not suspected (no). See below for further instructions on the assessment of causality.
- The start and end dates, unless unresolved at the final safety follow-up visit.
- The action taken with regard to study treatment as a result of the AE/SAE(s).
- The event outcome (eg, not recovered/not resolved, recovered/resolved, recovering/resolving, recovered/resolved with sequelae, fatal, unknown).

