8.2.2. Adverse Events of Special Interest

Adverse events of special interest will include irAEs and IRRs; these events will be coded according to MedDRA along with all other AEs.

Immune-related AEs will be using the sponsor-predefined PTs based on the immune checkpoint inhibitor class regardless of the investigator's assessment of causality. The sponsor-assessed irAEs will be summarized by grouped term, PT, and severity grade (ie, CTCAE Grades 1, 2, 3, 4, 5).

Infusion-related reactions will be identified using sponsor-predefined PTs indicating a diagnosis of IRRs or symptoms potentially associated with IRRs. Diagnosis of infusion reaction occurring anytime of the treatment period, or symptom of infusion reaction that occurred within 1 day of infusion, and resolved within 2 days from AE onset, are captured as infusion reactions. The sponsor-assessed IRRs will be summarized by grouped term, PT, and severity grade (ie, CTCAE Grades 1, 2, 3, 4, 5).

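### The 2-day resolution condition leaves fatal, unresolved and longer-lasting symptom-coded infusion reactions out of the IRR summaries

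*SAP*

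**What the plan says.** SAP 8.2.2 identifies infusion-related reactions (IRRs) from sponsor-defined preferred terms, by two routes. The first is a "Diagnosis of infusion reaction occurring anytime of the treatment period", with no limit on duration. The second is a "symptom of infusion reaction that occurred within 1 day of infusion, and resolved within 2 days from AE onset". The results are to be tabulated by all five CTCAE grades. SAP 8.2.3 adds a summary by maximum severity and an infusion-related line in the overall AE summary. SAP Appendix A lists Tables 3.2.18.1 to 3.2.18.3 for these summaries and marks all three for the DSMB package.

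Protocol 9.3 decides which route an event takes: "Whenever possible, the diagnosis (not the individual signs/symptoms) will be documented as the AE/SAE". Where no clear diagnosis can be made, each sign or symptom is entered as its own event. The same section has each change in severity entered as a separate AE.

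**The concern.** Case status on the symptom route depends on how the event turned out, not only on its timing relative to the infusion. A symptom that begins within a day of infusion and then persists, never resolves or ends in death is not an IRR under the SAP. The same symptom clearing in 2 days is one. A severity table built on that definition can lose events from its upper rows, and for symptom-coded events the Grade 5 row cannot be filled at all.

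Safety of TG2 and TG3 against TG1 is a secondary objective, and the IRR tables are where a reader or the DSMB would look for the infusion tolerability of the added antibodies.

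**Working it through.** No figure in the plan bears on this point, so the check is whether each grade in Protocol Table 10 entails failure of the SAP condition.

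**Grade definitions (Protocol 6.5.2, Table 10)**
- Grade 3 has three alternative routes. One is "Prolonged (ie, not rapidly responsive to symptomatic medication and/or brief interruption of infusion". The others are "recurrence of symptoms following initial improvement; hospitalization indicated for other clinical sequelae". None states a number of hours or days.
- Grade 4 is "Life-threatening; pressor or ventilatory support indicated", again with no duration.

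**Outcome under SAP 8.2.2**

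| Event | Counted as an IRR? |
|---|---|
| Symptom-coded, onset within 1 day, Grade 1 to 4, resolved within 2 days | Yes |
| Symptom-coded, onset within 1 day, Grade 1 to 4, lasting more than 2 days | No |
| Symptom-coded, onset within 1 day, any grade, never resolved | No |
| Symptom-coded, onset within 1 day, Grade 5 | No, since it cannot resolve |
| Diagnosis-coded, any grade or duration | Yes |

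What removes an event is duration, non-resolution or death. Grade alone does not, except Grade 5. Mild symptoms that linger are removed as well.

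**Two gaps in the rule**
- Because each severity change is a separate record, the result depends on an unstated choice. Take a symptom that starts on the infusion day at Grade 3, eases to Grade 1 within 2 days and clears only later. If the end of the Grade 3 record is treated as resolution, it is counted; judged on the whole episode, it is not.
- SAP 8.2.1 sends unresolved missing or partial dates to Section 4.1.4. That section covers cancer diagnosis, last dose and death dates, but not AE end dates. An event with no end date cannot be shown to have resolved.

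**How common is the symptom route?** Protocol 2.2.4 gives the only relevant triplet data: 4 of 17 participants had an infusion-related event, and 2 of them had the IRR term. So 4 − 2 = 2 entered through symptoms (pyrexia, chills) alone. At those rates, with 54 per group:
- any infusion-related event: 4/17 × 54 = 12.7;
- symptom-only: 2/17 × 54 = 6.4.

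These are participants with events of any grade to whom the rule would apply. They are not participants lost. The same section reports every triplet infusion event as nonserious and Grade 1 or 2, which is 0 of 17 at Grade 3 or higher, and gives no durations. Nor does it say whether a 2-day condition had already been applied in producing the 4 of 17.

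**The case against.** A reader might infer that, because Table 10 calls a Grade 3 reaction prolonged, Grade 3 symptom-coded reactions are excluded by definition. The documents do not support that. The term is explained relative to symptomatic medication and a brief interruption of the infusion, so a reaction lasting hours can be Grade 3 and still meet the 2-day rule. It is also one of three routes. Moreover, Table 10 grades a recognized infusion reaction, which Protocol 9.3 would normally have recorded as the diagnosis and so exempt from the limit.

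Two further arguments have weight. Symptom terms such as pyrexia are non-specific, and the Phase 1 serious events included sepsis and COVID-19, so a short resolution window is a reasonable way to keep infections out. And nothing is hidden. The SAP tabulates all, Grade 3 or higher, serious and fatal TEAEs, and those leading to infusion interruption or discontinuation, with no duration filter. The DSMB package includes the Grade 3 or higher, serious, interruption and discontinuation tables, the death summary and the fatal AE listing.

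What stands is narrower. Those tables do not identify an event as infusion-related, so they do not repair the IRR tables. The specificity argument also justifies a window for mild symptoms better than it justifies dropping a severe or fatal event that began within a day of infusion.

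**Conclusion.** The point holds as a gap in the case definition. On the literal text, symptom-coded reactions that are fatal, unresolved or longer than 2 days cannot enter IRR summaries that are meant to report Grades 1 to 5. Only fatal and never-resolved symptom-coded events are excluded by definition; for Grades 1 to 4, exclusion depends on the actual course of the event.

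Its size cannot be estimated. The 6 or so of 54 worked out above describe exposure to the rule, rest on two Phase 1 participants, and assume that this trial's sites record symptoms as often as Phase 1 sites did.

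A reader might also infer that an IRR excess in TG2 or TG3 is bound to be understated. That would need the combination groups to have more long-lasting symptom-coded reactions than TG1. The documents contain no durations and no comparative data, so neither the size nor the direction of a between-arm effect is shown.

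Safety carries no hypothesis test in this trial, so no formal conclusion is affected. This is an inexpensive improvement to a descriptive safety table.

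**What to change.** In SAP 8.2.2, for Grade 3 or higher symptom terms on the sponsor's list with onset within 1 day of infusion, count the event whatever its duration or outcome. Keep the 2-day condition for Grades 1 and 2. If the sponsor prefers to retain the current definition as the main one, add an IRR summary by grade without the resolution condition.

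In either case, state that the 2-day clock runs on the whole episode, from first onset to final resolution, and not on severity-split records. State also how ongoing events and missing end dates are classified.

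The cost is a few sentences and one derivation change. Protocol 9.3 already collects AE start and end dates, so no new data are needed. The downside is that an occasional severe event of other cause, such as an infection starting within a day of dosing, will be labelled an IRR. All three groups follow the same blinded infusion schedule, so such chance labelling should fall about equally across them. The additional-summary option avoids changing the main table.

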8.2.3. Adverse Event Summaries

An overall summary of AEs by treatment group will include the following:

- Number (%) of participants reporting any TEAEs
- Number (%) of participants reporting any serious TEAEs
- Number (%) of participants reporting any Grade 3 or higher TEAEs
- Number (%) of participants who had any treatment related TEAEs
 - Number (%) of participants who had any TEAEs related to retifanlimab
 - Number (%) of participants who had any TEAEs related to INCAGN02385/placebo for INCAGN02385
 - Number (%) of participants who had any TEAEs related to INCAGN02390/placebo for INCAGN02390
- Number (%) of participants who had any treatment-related serious TEAEs
- Number (%) of participants who had any treatment-related Grade 3 or higher TEAEs
- Number (%) of participants who had a TEAE leading to study drug infusion interruption, next scheduled dose delay, or discontinuation
 - Number (%) of participants who had a TEAE leading to study drug infusion interruption
 - Number (%) of participants who had a TEAE leading to next scheduled dose delay of study drug
 - Number (%) of participants who had a TEAE leading to permanently discontinued study drug
- Number (%) of participants who had any immune-related TEAEs – sponsor-assessed
- Number (%) of participants who had any infusion-related TEAEs – sponsor-assessed
- Number (%) of participants who had a fatal TEAE

The following summaries will be produced by MedDRA term (if 10 or fewer participants appear in a table, a listing may be appropriate):

- Summary of TEAEs by SOC and PT
- Summary of TEAEs by PT in decreasing order of frequency
- Summary of TEAEs by SOC, PT, and maximum severity
- Summary of Grade 3 or higher TEAEs by SOC and PT
- Summary of Grade 3 or higher TEAEs by PT in decreasing order of frequency
- Summary of serious TEAEs by SOC and PT
- Summary of serious TEAEs by PT in descending order of frequency
- Summary of treatment-related TEAEs by SOC and PT
- Summary of treatment-related TEAEs by PT in decreasing order of frequency
- Summary of Grade 3 or higher treatment-related TEAEs by SOC and PT
- Summary of treatment-related serious TEAEs by SOC and PT
- Summary of TEAEs with a fatal outcome by SOC and PT
- Summary of TEAEs leading to study drug infusion interruption by SOC and PT
- Summary of TEAEs leading to next scheduled dose delay of the study drug by SOC and PT
- Summary of TEAEs leading to discontinuation of study drug by SOC and PT
- Summary of immune-related TEAEs by grouped term and PT (sponsor-assessed)
- Summary of immune-related TEAEs by PT in descending order of frequency (sponsor-assessed)
- Summary of immune-related TEAEs by grouped term, PT, and maximum severity (sponsor-assessed)
- Summary of infusion-related TEAEs by grouped term and PT (sponsor-assessed)
- Summary of infusion-related TEAEs by PT in descending order of frequency (sponsor-assessed)
- Summary of infusion-related TEAEs by grouped term, PT, and maximum severity (sponsor-assessed)

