10.1. Sample Size Determination

The sample size calculation is based on the primary endpoint of PFS. Approximately 162 participants will be randomized in a 1:1:1 ratio into TG1:TG2:TG3. The study is event-driven and will be complete after approximately 94 PFS events have been observed between TG1 and TG2 or between TG1 and TG3 (approximately 140 PFS events across the 3 treatment groups). Based on a target of 94 PFS events for all participants at the final analysis between TG1 and TG2 or between TG1 and TG3 (approximately 140 PFS events across the 3 treatment groups), which is expected to occur about 20 months from the start of enrollment, the study has approximately 80% power to detect an HR of 0.6 at an overall alpha level of 5% (1-sided) favoring one of the combination therapies with the assumption of study parameters as specified in Table 17 for PFS.

The sample size and power calculations were performed in R package "gsDesign."

Table 17: Sample Size Assumptions for Progression-Free Survival

Variable	Assumptions
Median PFS in TG1 (All participants)	3 months ^a
Randomization ratio	1:1:1
Assumed HR (All participants)	0.6
Enrollment duration	12 months
Follow-up for PFS	8 months
Assumed annual dropout rate	1%

^a Burtneess et al 2019.

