2.2. Study Objectives and Endpoints

[Table 1](#) presents the primary and secondary objectives and endpoints.

Table 1: Objectives and Endpoints

Objectives	Endpoints
Primary	
To determine the efficacy of the combinations of retifanlimab + INCAGN02385 (TG2) and retifanlimab + INCAGN02385 + INCAGN02390 (TG3) compared with retifanlimab alone (TG1) in the overall study population.	Progression-free survival, defined as the interval between the date of randomization and the earliest date of disease progression, based on investigator assessment per RECIST v1.1, or death due to any cause.
Secondary	
To assess disease response using RECIST v1.1 in TG2 and TG3 compared with TG1.	
 Objective response, defined as having a CR or PR, determined based on investigator assessment per RECIST v1.1. DOR, defined as the time from earliest date of disease response (CR or PR) until earliest date of disease progression, based on investigator assessment per RECIST v1.1, or death from any cause if occurring sooner than progression. Disease control, defined as having CR, PR, or SD (≥ 6 months) as best response, based on investigator assessment per RECIST v1.1.
To determine the OS of TG2 and TG3 compared with TG1.	Overall survival, defined as the interval between the date of randomization until death due to any cause.
To determine the safety of TG2 and TG3 compared with TG1.	
 AEs, assessed in body systems with symptoms, through physical examinations, changes in vital signs and ECGs, and through clinical laboratory blood sample evaluations. Impact on study treatment, assessed by treatment interruptions, dose delays, and withdrawal of study treatment due to AEs.
Exploratory	

Table 1: Objectives and Endpoints (Continued)

Objectives	Endpoints
Exploratory (continued)	

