3.2. Sample Size Considerations and Timing of Final Analysis

The sample size calculation is based on the primary endpoint of PFS. Approximately 162 participants will be randomized in a 1:1:1 ratio into TG1:TG2:TG3.

The final analysis will be performed after approximately 94 PFS events have been observed between TG1 and TG2 or between TG1 and TG3 (approximately 140 PFS events across the 3 treatment groups) or the last participant has been followed up for at least 8 months after randomization, whichever is earlier.

The sample size and power calculations were performed in R package "gsDesign" and as tabulated in [Table 2](#).

Table 2: Boundary Properties for Final Analysis of Progression-Free Survival Based on Potential Alpha Levels

Analysis	Value	$\alpha = 0.05$ (1-Sided)	$\alpha = 0.10$ (1-Sided)
Final	Z	1.645	1.2816
N: 108	p (1-sided)	0.0500	0.1000
Events: 94 (approximately 140 events across 3 treatment groups)	~HR at bound	0.7120	0.7670
Month: 20	P (Cross) if HR = 1	0.0500	0.1000
	P (Cross) if HR = 0.6	0.8000	0.8840

Based on a target of 94 PFS events for all participants at the final analysis between TG1 and TG2, which is expected to occur about 20 months from the start of enrollment if 108 participants are enrolled within 12 months, the study has approximately 80% power to detect an HR of 0.6 at an alpha level of 5% (1-sided), favoring a combination therapy versus TG1 with the assumption of study parameters as specified in Table 17 of the Protocol. When the 1-sided alpha level is 10%, the statistical power is 88.4%. The same assumption and sample size calculation approach is followed for TG3 and TG1.

The total sample size across the 3 treatment groups is calculated using 1.5 times the sample size from 2 treatment groups.

In case of delay in achieving the targeted number of PFS events, the primary analysis may be conducted when the last participant has been followed up for at least 8 months after randomization, even if the targeted number of events is not reached. In this case, the median PFS follow-up time across the blinded treatment groups will be quantified using the reverse Kaplan-Meier method and monitored by the study team. The study team will evaluate if the lower limit of the 95% CI for the median PFS follow-up time is achieved after 8 months.

[Table 3](#) shows the boundary properties for scenarios when the number of PFS events is approximately 108, 123, and 130 across the 3 treatment groups.

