8.2. Adverse Events

8.2.1. Adverse Event Definitions

All safety analyses will be conducted using the safety population.

A TEAE is any AE either reported for the first time, or worsening of a pre-existing event, after first dose of study drug until 90 days after the last dose of study drug. Analysis of AEs (as discussed below) will be limited to TEAEs, but data listings will include all AEs regardless of their timing in relation to study drug administration, flagging those that are not TEAE. For purposes of analysis, all AEs will be considered TEAEs unless the AE can unequivocally be defined as not treatment-emergent.

Adverse events will be tabulated by MedDRA SOC and PT. Severity of AEs will be graded using the NCI CTCAE v5.0 using Grades 1 through 5. The CTCAE reporting guidelines and grading details are available on the Cancer Therapy Evaluation Program website.

The subset of AEs considered by the investigator to be related to study drug will be considered to be treatment-related AEs. If the investigator does not specify the relationship of the AE to study drug, the AE will be considered to be treatment-related. The incidence of AEs and treatment-related AEs will be tabulated. In addition, serious TEAEs will also be tabulated

Any missing onset date, causality, or severity must be queried for resolution. Unresolved missing or partial dates will be handled using the rules described in Section 4.1.4. Unresolved missing causality and severity will be handled according to the following rules:

- An unresolved missing causality will be considered treatment-related.
- An unresolved missing severity will be identified as an unknown severity.

The number and percentage (%) of participants reporting any TEAEs, any serious TEAEs, any Grade 3 or higher TEAEs, any treatment-related TEAEs, any treatment-related serious TEAEs, any treatment-related Grade 3 or higher TEAEs, any fatal TEAEs, and any TEAEs leading to treatment interruption/discontinuation will be tabulated by MedDRA SOC and PT. Data listings will include all AEs regardless of their timing to study drug administration.

Infusion-related reactions, as well as irAEs, may be summarized separately.

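### Adverse events are compared with TG1 only as crude percentages, so if a combination prolongs PFS as assumed, equal AE hazards may show as an excess of about 3 to 7 points

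*SAP*

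**What the plan says.** SAP 2.2 (Table 1) sets a comparative safety objective: "To determine the safety of TG2 and TG3 compared with TG1".

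The outputs for it are counts and percentages. The overall summary in SAP 8.2.3 starts with "Number (%) of participants reporting any TEAEs" and continues in the same form for serious, Grade 3 or higher, treatment-related, immune-related, infusion-related and discontinuation events. SAP 8.2.1 says of the participant counts that "any fatal TEAEs, and any TEAEs leading to treatment interruption/discontinuation will be tabulated by MedDRA SOC and PT". Protocol 10.4.4 and the 3.2.x tables in SAP Appendix A follow the same pattern. The visible text plans no person-time rate, time-to-first-event analysis, cumulative incidence or fixed-window AE summary. SAP Table 5 gives the AE metric as Rate and does not define it.

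The TEAE window runs "after first dose of study drug until 90 days after the last dose of study drug". Under Protocol 7.1.1, confirmed or unequivocal progression is a mandatory reason to stop treatment, and treatment is capped at 2 years.

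Exposure is summarised by study drug in SAP 6.4, including duration categories from 3 to 24 months, but is not linked to AE incidence.

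On efficacy, Protocol 10.1 states that "the study has approximately 80% power to detect an HR of 0.6", with an assumed TG1 median PFS of 3 months.

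**The concern.** A crude percentage answers how many participants had an event while they were under observation. When arms are observed for different lengths of time, a difference in percentages mixes the AE hazard with the length of the window. Here the window depends on time on treatment, which depends largely on progression, which the combinations are meant to delay. The distortion would therefore appear when a combination works, which is when its safety relative to TG1 matters most for the benefit/risk judgement. It acts in the same direction on every category whose risk persists over time.

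**Working it through.** **1. Reproduce the design figure.** SAP Table 2 gives power 0.8000 (one-sided alpha 0.05) and 0.8840 (alpha 0.10) for 94 events and HR 0.6. Schoenfeld: power = Φ(√94/2 × |ln 0.6| − z) = Φ(2.476 − z). With z = 1.645 this is 0.797; with z = 1.2816 it is 0.884. With exponential PFS, 54 per arm, uniform 12-month accrual, 8 months of further follow-up and 1% annual dropout, expected events at month 20 are 96.1 for a pair and 141.2 for three arms, against 94 and about 140 planned. The inputs are consistent with the plan.

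**2. Implied PFS.** TG1 hazard = ln 2/3 = 0.231 per month. Combination hazard = 0.6 × 0.231 = 0.139, so the median is ln 2/0.139 = 5.0 months.

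**3. TEAE window.** Assumptions: time on treatment T is exponential with the PFS hazard, capped at 24 months; the window is T + 90/30.4375 = T + 2.96 months (month length from SAP 6.4), cut off at C, uniform on 8 to 20 months after randomization (12-month enrolment, final analysis at about month 20). Means from 2,000,000 draws, TG1 versus combination:

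| | Final analysis | Full follow-up |
|---|---|---|
| Time on treatment (months) | 4.1 vs 6.1 (ratio 1.48) | 4.3 vs 7.0 (1.61) |
| TEAE window (months) | 6.8 vs 8.4 (1.23) | 7.3 vs 9.9 (1.36) |

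The common 90 days dilutes the ratio.

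**4. Crude percentages with the same constant AE hazard h in both arms.** Crude risk = E[1 − exp(−hW)], where W is the window. The documents give no AE hazards for this trial, so a range is assumed. SE = √[p1(1−p1)/54 + p2(1−p2)/54].

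| h per month | Final analysis: TG1 vs combination (excess) | SE | Full follow-up (excess) |
|---|---|---|---|
| 0.02 | 12.6 vs 15.2% (2.7) | 6.7 | 13.2 vs 17.4% (4.1) |
| 0.05 | 28.0 vs 33.1% (5.1) | 8.9 | 29.1 vs 36.4% (7.3) |
| 0.10 | 47.0 vs 53.7% (6.7) | 9.6 | 48.1 vs 56.7% (8.6) |
| 0.50 | 92.8 vs 95.0% (2.2) | 4.6 | 92.8 vs 95.1% (2.3) |

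Hand check, full follow-up, h = 0.10, ignoring the cap: 1 − exp(−0.10 × 2.96) × 0.231/(0.231 + 0.10) = 1 − 0.744 × 0.698 = 48.1%.

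**5. Early-onset events.** With h = 0.10 confined to the first 3 months, the crude figures at the final analysis are 25.9% in both arms. Confined to the first 6 months, they are 39.9 vs 41.7%.

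**6. Behaviour of the person-time rate.** With constant h = 0.10, first events per 100 patient-months are 10.0 in both arms, so the artefact disappears. With identical risk in the first 3 months only, the rate is 4.77 (TG1) vs 3.92 (combination) at the final analysis, which falsely favours the combination. If the combination's early hazard is truly 30% higher (0.13 vs 0.10), full-follow-up rates are about 4.5 in both arms, while the crude percentages are about 26 vs 32%.

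Competing deaths and repeated events per participant were not modelled.

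**The case against.** A reader might infer that the design assumes much longer treatment on the combinations and that equal toxicity will therefore look like excess toxicity. The documents do not support that. Protocol 10.1 assumes a PFS median and a hazard ratio, not a treatment duration. Treatment may continue past first radiologic progression (Protocol 6.5.5), and all three drugs stop when toxicity ends treatment (Protocol 6.5.1), which could shorten exposure in a more toxic arm and reverse the bias. The TEAE window, which is what matters for these tables, differs by much less than time on treatment.

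Several further points stand. The artefact is below one standard error with 54 per arm. The any-TEAE line is close to saturation: Protocol 2.2.2 to 2.2.4 report a TEAE in every participant on each new agent alone and in 94.1% on the triplet. AEs carry no hypothesis, SAP 10.2 describes the study as not registrational, and crude incidence is a valid description of each regimen as given. The exposure tables let a reader see unequal exposure, so the plan does not leave it hidden.

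The most serious objection is that person-time rates alone could hide real early toxicity, as step 6 shows. That also stands, and it shapes the remedy.

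None of this removes the gap. Seeing unequal exposure in a separate table is not the same as allowing for it, and low precision is no reason to keep an avoidable bias. Protocol 6.5.3 also notes that immune-related events can arise soon after the first dose or months after the last, so risk cannot be assumed to be wholly early.

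**Conclusion.** The point holds in a limited form. The planned AE comparison with TG1 takes no account of time at risk. If the true HR is near 0.6, time on treatment tracks PFS and AE hazards are roughly constant at 0.02 to 0.10 per month, crude percentages may overstate combination toxicity by about 3 to 7 points at the final analysis, or 4 to 9 with full follow-up. The artefact vanishes if exposure is equal. It is nil or small for early-onset events and for any TEAE, so the lines that matter are serious, Grade 3 or higher, immune-related and discontinuation events. It would be too strong to conclude that the safety comparison is invalid or that an observed excess could be dismissed as an artefact. This is an interpretive gap in a descriptive Phase 2 analysis, not an error in a stated figure.

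**What to change.** Keep the crude tables. For serious, Grade 3 or higher, sponsor-assessed immune-related and discontinuation TEAEs, add by group:

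- cumulative incidence of the first event at fixed times, for example 3 and 6 months;
- first events per 100 patient-months at risk, censored at the earlier of last dose + 90 days or data cutoff, with the difference from TG1 and its 95% CI.

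Define Rate in SAP Table 5 accordingly. State in SAP 8.2.3 that the person-time rate is neutral only under a roughly constant hazard, that it understates toxicity in the longer-exposed arm when risk is early, and that it must be read with the fixed-time and crude figures.

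Cost: a cheap improvement, but not free. It needs a short SAP edit and a few extra tables built from dosing and AE dates already collected, with no change to study conduct. The downside is that the measures may disagree and will then need careful interpretation.
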